5.3.1.5 Communication Documentation form

The form will be completed by the clinician at each visit to document any communication by the subject (Group A and B) to the clinic or the manufacturer. Information collected will include the purpose of the communication and outcome.

5.3.1.6 Subject Service Satisfaction Survey

The in-house questionnaire will be completed by the subject to rate the service they have received by their provider at switch-on and 6 months (Group A and B).

Recipient Services post-call survey will be completed by subject to rate their experience with the video call (Group A).

5.3.1.7 Rehabilitation Screener

The clinician will use the screening tool based on the auditory hierarchy to evaluate Group A subject progress in the detection, identification, discrimination and comprehension of auditory stimuli. A list of resources will be provided to the subject for take home use.

5.3.1.8 Materials/Tools Questionnaire

The in-house questionnaire will be completed by the professional to evaluate the subject's ability to complete basic device use and accessory use tasks at switch-on, 3 months and 6 months (Group A and B).

5.4 Pre-operative Procedure

5.4.1 Preoperative Candidacy Evaluation

5.4.2 Informed Consent

A preoperative interview (as part of the informed consent process) will be conducted by the surgeon and/or audiologist to inform the candidate about all aspects of implantation with a cochlear implant, study goals and requirements, as well as the evaluation schedule. The potential limitations and advantages of cochlear implantation shall also be explained.

After reviewing the Informed Consent Form, the candidate will be given the opportunity to review and ask questions about the Informed Consent Form and/or the study prior to signing the Informed Consent Form. The candidate will be offered the opportunity to take the form home to discuss with family members should they choose to do so. If they sign the Informed Consent Form, the candidate will then be given a copy of the signed Informed Consent Form to take home.

A candidate is not considered enrolled until a properly executed Informed Consent Form has been obtained along with the results of the preoperative candidacy evaluation. CNC, AzBio at + 10 SNR, SSQ-12 and COSI completed prior to consent within 90 days will be accepted as part of the pre-op candidacy evaluation.

5.4.3 Candidacy Baseline Assessment

The clinic will administer their typical candidacy baseline assessment for patients receiving a cochlear implant as standard of care. In addition, they will administer the following, if not part of the standard battery:

- New Model (Group A) and Traditional Model (Group B)
 - CNC Words: Two lists at 60 dBA with an appropriately fit hearing aid in the unilateral condition (contralateral ear plugged)
 - AzBio Sentences in Noise at 60 dBA at +10 dB S0N0 presented in the sound field for the everyday listening condition.
 - Patient reported outcomes:
 - SSQ-12
 - COSI
 - Hearing History: Information collected from the subject regarding the type and duration of their hearing loss.
 - Demographics: Characteristics of the subject population to include race, ethnicity and gender etc.
 - Device History: Current and previous use of hearing aids
 - Medical History: current or past medical conditions or surgical history relevant to the conduct of the study
- Eligibility: confirmation subject meets inclusion and exclusion criteria
- Randomization: Upon randomization, Group A subjects will receive the following:
 - A take home packet (at the candidacy evaluation or post-surgery) prior to the switch-on to provide them with information they will review as part of the self- learning.
 - Written instructions for scheduling a support call with Cochlear Recipient Services for counselling on external equipment and cochlear implant system. Call will be scheduled 2 weeks following initial activation.

5.5 Post-operative Procedure

5.5.1 Initial Activation of Sound (Switch-on)

At the initial activation appointment, the following procedures will be completed:

- New Model (Group A):
 - Creation of AutoMAPs with AI
 - Self-directed device use using study materials and video conference call with Cochlear Recipient Services
 - Clinician reported Materials/Tools questionnaire
 - An anonymized .cdx file will be provided to the study sponsor
 - Subject Service Satisfaction Survey
- Traditional Model (Group B):
 - Programming and counselling as defined by Center
 - Complete Clinician reported Materials/Tools questionnaire
 - An anonymized .cdx file will be provided to the study sponsor
 - Subject Service Satisfaction Survey

5.5.2 1-2 weeks Post Activation

- Traditional Model (Group B)
 - Programming and/or counselling as defined by Center
 - An anonymized .cdx file will be provided to the study sponsor

5.5.3 One Month Post activation

At 1-month post activation, the following procedures will be completed:

- New Model (Group A)
 - Confirm Device use through usage data screen in Custom Sound
 - Optional: AutoNRT if not collected in the OR at the time of surgery
 - Evaluate highest tolerable AutoMAP

- Administer psychoacoustic tests using direct connect:
 - Complete Audiogram – obtain FOX (AI) advice
 - Complete phoneme discrimination and obtain FOX (AI) advice
 - Provide AI MAP to subject for take home use
- Complete Rehabilitation Screener and provide list of resources
- Provide appropriate accessory materials for self-driven learning based on goals of COSI and ability of subject
- Communication documentation form
- An anonymized .cdx file will be provided to the study sponsor
- Traditional Model (Group B)
 - Programming and/or counselling as defined by Center
 - Communication documentation form
 - An anonymized. cdx file will be provided to the study sponsor

5.5.4 Three Month Post activation

At 3 months post activation, the following procedures will be completed:

- New Model (Group A)
 - Confirm Device use through usage data screen in Custom Sound
 - Administer psychoacoustic tests to include:
 - Any pending outcomes requests from 1-month visit
 - Loudness scaling
 - Speech Audiometry
 - Obtain FOX (AI) advice
 - Review CNC performance at 70dB on speech audiometry to determine if recipient tracking to ≥ 20 pre-post improvement on CNC words
 - If meets above criteria and AI has no other recommendations (Green/Teal FOX): Provide AI MAP for take home use. If recommendations have been made, complete at 6 month visit

as part of Pending Outcomes. Provide the MAP with the best outcome for take home use.

- If **not** completed at 1 month, provide appropriate accessory materials for self-driven learning based on goals of COSI.
- If does **not** meet above criteria (≥ 20 CNC words) and/or AI has made modifications to the fitting and wants additional outcome measures, complete as requested.
 - Obtain FOX (AI) advice to see if the outcome has improved. Provide the MAP with the best outcome for take home use.
 - If **not** completed at 1 month, provide appropriate accessory materials for self-driven learning based on goals of COSI
 - Complete Clinician reported Materials/Tools questionnaire
 - Communication Documentation form
 - Update COSI (Degree of Change)
 - An anonymized .cdx file will be provided to the study sponsor
 - CNC Words: Two lists of 50 monosyllabic words at 60 dBA in the soundfield using a configuration of speech at 0° azimuth in quiet for the implanted ear (contralateral ear plugged)
- Traditional Model (Group B)
 - Programming and/or counselling as defined by Center
 - Communication documentation form
 - Update COSI (Degree of Change)
 - CNC Words: Two lists of 50 monosyllabic words at 60 dBA in the soundfield using a configuration of speech at 0° azimuth in quiet for the implanted ear (contralateral ear plugged)
 - An anonymized. cdx file will be provided to the study sponsor

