5.3 Description of Study Measures

5.3.1 Patient Outcome Measures

Psychophysical Tests

This term is an overarching name for the following tests: Speech audiometry, phoneme discrimination, loudness scaling, and audiometry. All tests are completed via a direct connect system and collect data regarding detection, discrimination and identification of sound through the cochlear implant. Results from these tests are incorporated into recommendations for the AI MAP. Specific tests within the psychoacoustic test battery to be completed at each study visit are based on recommendations through the AI.

The following psychoacoustic tests will be completed through a direct connect system for the new model group (Group A):

- Speech audiometry

For this study, 25 CNC words randomly selected from each list will be administered in quiet at each level equal to 40, 55, 70 and 85dB SPL for speech audiometry. Testing will be completed and scored as the percentage of correctly repeated phonemes. An average phoneme score will be calculated within the test module, across the four presentation levels.

- Phoneme discrimination

The phoneme discrimination test is performed using up to 20 pre-defined speech sound contrasting pairs (a-r, u-ʃ, u-a, u-i, i-a, o-a, i-e, m-z, s-ʃ, e-a, u-o, ə-a, ə-o, ə-e, ə-i, z-s, v-z, ə-u, u-y, y-i). Phoneme pairs have been

established as linguistically representative and are tested at 70 dB HL in an oddity paradigm (Govaerts et al., 2006). Subjects will provide a behavioral response (e.g., hand raise or verbal response) if a discrimination is recorded for the phoneme contrast. Two correct responses are required to be considered as correct identification as scored by the Investigator. Training for at least one phoneme pair will be completed for each study visit to ensure familiarity with the test.

- Loudness scaling

Loudness scaling testing is completed by presentation of one-third octave narrow band noises centered at 250, 1000, and 4000 Hz. A 1876 ms duration stimulus will be presented randomly twice at 5dB increments between 30 and 80dB HL. Loudness will be scored on a visual analogue scale ranging from 0 (inaudible) to 6 (too loud) by the subject. (Varenburg et al. 2011, Govaerts et al, 2006, Hereen et al., 2012).

- Audiometry

Aided audiometric thresholds will be obtained using narrow band noise and the standard audiometric technique at the following frequencies 250, 500, 1000, 2000, 3000, 4000, 6000, Hz.

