In addition, one list of AzBio +10 S/N at S0N0 in the sound field in the two-ear listening condition using the subjects preferred noise program and accessory if appropriate will be completed in a calibrated sound booth.

Two lists of CNC words of 50 monosyllabic words in CD format will be administered in quiet at a level equal to 60dBA in the soundfield and scored as total number of words correct, which will be expressed as a percentage correct for this study. Subjects will be tested in the unilateral condition using a configuration of speech at 0° azimuth in quiet in a calibrated sound booth.

The following speech perception tests will be administered to the traditional model group (Group B):

- One list of AzBio +10 S/N at S0N0 in the sound field in the two-ear listening condition using the subjects preferred noise program.
- Two lists of CNC words of 50 monosyllabic words in CD format will be administered in quiet at a level equal to 60dBA in the soundfield and scored as total number of words correct, which will be expressed as a percentage

correct for this study. Subjects will be tested in the unilateral condition using a configuration of speech at 0° azimuth in quiet in a calibrated sound booth.

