5.5.5 Six Months Post activation

At 6 months post activation, the following procedures will be completed:

- New Model (Group A)
 - Confirm Device use through usage data screen in Custom Sound
 - Administer psychoacoustic tests to include:
 - Any pending outcomes requests from 3-month visit
 - Speech Audiometry
 - Obtain FOX Advice
 - Review CNC performance at 70dB on speech audiometry to determine if recipient tracking to ≥ 30 pre-post improvement on CNC words
 - If subject meets above criteria and AI has no other recommendations (Green/Teal FOX): Provide AI MAP for take home use.
 - Complete patient reported COSI and SSQ-12
 - Complete Clinician reported Materials/Tools questionnaire
 - Complete Clinician satisfaction questionnaire
 - Complete subject Service Satisfaction Questionnaire
 - Evaluate hearing options for contralateral ear
 - CNC Words: Two lists of 50 monosyllabic words at 60 dBA in the soundfield using a configuration of speech at 0° azimuth in quiet for the implanted ear (contralateral ear plugged)
 - AzBio Sentences in Noise at 60 dBA at +10 dB S0N0 presented in the soundfield for the everyday listening condition
 - Communication Documentation form
 - An anonymized .cdx file will be provided to the study sponsor
 - If the subject does **not** meet above criteria (≥ 30 CNC words) and AI has made modifications to the fitting and wants additional outcome measures, complete as requested.

- Complete patient reported COSI and SSQ-12
- Complete Clinician reported Materials/Tools questionnaire
- Complete clinician satisfaction questionnaire
- Complete subject Service Satisfaction Questionnaire
- Evaluate hearing options for contralateral ear
- CNC Words: Two lists of 50 monosyllabic words at 60 dBA in the soundfield using a configuration of speech at 0° azimuth in quiet for the implanted ear (contralateral ear plugged)
- AzBio Sentences in Noise at 60 dBA at +10 dB S0N0 presented in the soundfield for the everyday listening condition
- An anonymized .cdx file will be provided to the study sponsor.
- If CNC word score at 70 dB on speech audiometry remains less than 30% after completing the above steps, it is recommended the patient be seen in 1 month using standard clinical procedures using Custom Sound directed by CTM Cochlear staff.
- Traditional Model (Group B)
 - Programming and/or counselling as defined by Center
 - Communication documentation form

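### Group A's 3- and 6-month CNC milestone rests on a 70 dB test that the protocol scores in phonemes in one section and calls a word score in another, set against an unnamed, non-comparable pre-operative value

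*Protocol*

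**What the plan says.** **The milestone.** Protocol section 5.5.4 (3 months, Group A) instructs: "Review CNC performance at 70dB on speech audiometry to determine if recipient tracking to" a change of at least 20. Section 5.5.5 (6 months, Group A) repeats this with at least 30, described as "pre-post improvement on CNC words". Both sections then restate the criterion as a number of CNC words, with no percent sign. Sections 3 and 10.1 give the same milestones in percent.

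**The test it is judged on.** Section 5.3.1 says of the psychoacoustic battery that "All tests are completed via a direct connect system". For speech audiometry, "25 CNC words randomly selected from each list will be administered in quiet at each level", at 40, 55, 70 and 85 dB SPL. On scoring: "Testing will be completed and scored as the percentage of correctly repeated phonemes". The only summary described is this: "An average phoneme score will be calculated within the test module, across the four presentation levels".

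**The pre-operative test.** Section 5.4.3 lists "CNC Words: Two lists at 60 dBA with an appropriately fit hearing aid in the unilateral condition (contralateral ear plugged". Table 1 shows no other pre-operative CNC. Section 5.3.1 has the 60 dBA CNC given in the sound field as two lists of 50 words, "scored as total number of words correct, which will be expressed as a percentage".

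**The 6-month follow-on rule.** Section 5.5.5 ends the Group A pathway with a recommended return in 1 month if the 70 dB speech-audiometry result, there called a CNC word score, is still under 30%.

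**The concern.** A change score needs two measurements on one scale. Here the post value comes from a test that section 5.3.1 scores in phonemes, the criterion is a change in words, and the pre value is not identified. The one candidate for it is a different test. Section 5.5.5 then relabels the same 70 dB result as a word score and acts on it.

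The milestones are part of the intervention: sections 3 and 4 present the new model as standardised around outcome milestones. At 3 months the criterion helps decide whether tests requested by the AI are done in that timed visit or left for the 6-month visit. At 6 months the below-30% rule decides who is recommended to return. Clinicians at up to five sites could follow the text faithfully and classify the same patient differently.

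**Working it through.** The protocol states no calculated figure on this point, so there is none to reproduce. The check sets the definitions side by side and works out what follows.

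**1. The two measurements**

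| | Score used for the milestone | Only pre-operative CNC |
|---|---|---|
| Sections | 5.3.1 (speech audiometry), 5.5.4, 5.5.5 | 5.4.3; scoring and route from 5.3.1 |
| Level | 70 dB SPL | 60 dBA |
| Words | 25 | 2 × 50 = 100 |
| Scoring | percent phonemes (5.3.1); word score (5.5.5) | percent words |
| Route | direct connect | sound field |

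Level and list length differ whichever scoring applies. Scoring differs too if section 5.3.1 is followed.

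**2. Direction of the scoring error.** Let W be the proportion of words fully correct and q the mean proportion of phonemes correct within the missed words. Assume every word has the same number of phonemes. On the same responses the phoneme score is

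P = W + (1 − W) × q, with 0 ≤ q < 1.

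So P is never below W, and P − W = (1 − W) × q. Setting P against a word-scored baseline can only push the apparent gain up. Reading P against a below-30% rule can only flag the same number of patients or fewer.

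**3. Size.** The protocol does not give q, so the size cannot be derived. What can be shown is how large q would have to be to change a decision. Take a patient whose word score is 20% before and after (5 of 25 words), ignoring level and route:

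- apparent gain of 20 with no gain in words: q ≥ 20/80 = 0.25;
- apparent gain of 30 with no gain in words: q ≥ 30/80 = 0.375;
- phoneme score reaches 30%, so the return rule is not triggered: q ≥ (30 − 20)/80 = 0.125.

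These are break-even values, not estimates.

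**4. Unit.** On 100 words, 30 words and 30 percentage points are the same number. On 25 words they are not: each word is 100/25 = 4 points, and 30 words exceeds the 25 presented. Read literally on the 70 dB test, the 6-month criterion as restated in words cannot be met.

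**5. List length, if the 70 dB test were word-scored.** The binomial standard error at a 30% score is √(0.30 × 0.70/25) = 9.2 points on 25 words and √(0.30 × 0.70/100) = 4.6 points on 100 words. The post value would then be about twice as imprecise as a two-list score. This applies only under word scoring, and the error in step 2 only under phoneme scoring; the two are not added.

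**6. Gain criterion and below-30% rule.** With pre-operative score b on a common percent scale, any 6-month score from 30 up to, but not including, b + 30 misses the gain criterion without triggering the return rule. For b = 10 that is 30–39%; for b = 20, 30–49%; for b = 0 the two coincide. For example, 10% rising to 35% is a gain of 25: the milestone is missed and no return is recommended.

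**The case against.** **The test is a proxy.** The text speaks of tracking towards a gain, which can be read as an on-course check and not a computed difference. Direct connect tests hearing through the implant, so no such score can exist before activation, and out-of-booth testing is central to the new model. This stands as regards route: that difference is inherent and is not held against the plan. It does not name the pre value, say how a 70 dB result maps to a 60 dBA word score, or settle phonemes versus words.

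**The software may remove site variation.** Each site receives a laptop with the test software, and the module calculates the average score. The protocol does not say what the module shows for a single level, so variation between sites is possible but not demonstrated.

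**A reader might infer that the gain criterion and the below-30% rule contradict each other.** The protocol does not support that. Missing the gain leads to AI-requested testing at the visit; staying below 30% leads to a recommended return. Two rules with two consequences need not coincide. The protocol should say that they are separate, if they are.

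**A reader might also see a contradiction in the linking of the two conditions for further testing**, which is looser at 3 months (either or both) than at 6 months (both). The glossary defines pending requests as tests for the next visit, which fits deferral at 3 months, so this is not claimed as an error.

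**A reader might infer that trial endpoints are biased.** No endpoint or analysis in the protocol is defined on the 70 dB score. The CNC secondary endpoint can rest on the two-list 60 dBA test that both groups have pre-operatively and at 3 and 6 months. Extra testing also needs an AI request, so missing the milestone alone orders none. The return visit comes after the subject is deemed complete under section 9.1.

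**Conclusion.** The point holds as an internal inconsistency in the Group A care pathway. The scoring of the 70 dB test is stated in two incompatible ways, the pre-operative value is unnamed and its only candidate is not comparable, and the criterion appears both in percent and as a count that the 25-word test cannot supply at 6 months.

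Followed as written, the text tends to overstate improvement and to flag fewer low performers. The direction assumes equal phonemes per word, that sites score speech audiometry as section 5.3.1 says, and that the pre-operative lists are word-scored as section 5.3.1 says of the 60 dBA CNC. If the module in fact reports words at 70 dB, the scoring error disappears, but section 5.3.1 is then wrong and the differences in level and list length remain. The size cannot be obtained from the protocol.

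The CNC secondary endpoint is unaffected. Any effect on primary-endpoint minutes is indirect and unquantified. The point should be fixed, but it does not threaten the trial's analyses.

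**What to change.** The sponsor should reconcile sections 5.3.1, 5.4.3, 5.5.4 and 5.5.5, and align them with sections 3 and 10.1, so that:

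- the scoring of the 70 dB result (words or phonemes) and its unit are stated once and used throughout, including where the criterion is restated as a word count;
- the pre-operative value with which the 70 dB result is compared is named;
- the relation between the gain criterion and the below-30% rule is stated, including whether they are two separate rules.

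Which score, threshold or care rule stands is for the sponsor to decide; none is proposed here.

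The cost is a wording amendment and a clarification to sites. If the sponsor's decision changes which score steers care, that alters the Group A model and costs more than wording.

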5.5.5 Six Months Post activation

At 6 months post activation, the following procedures will be completed:

- New Model (Group A)
 - Confirm Device use through usage data screen in Custom Sound
 - Administer psychoacoustic tests to include:
 - Any pending outcomes requests from 3-month visit
 - Speech Audiometry
 - Obtain FOX Advice
 - Review CNC performance at 70dB on speech audiometry to determine if recipient tracking to ≥ 30 pre-post improvement on CNC words
 - If subject meets above criteria and AI has no other recommendations (Green/Teal FOX): Provide AI MAP for take home use.
 - Complete patient reported COSI and SSQ-12
 - Complete Clinician reported Materials/Tools questionnaire
 - Complete Clinician satisfaction questionnaire
 - Complete subject Service Satisfaction Questionnaire
 - Evaluate hearing options for contralateral ear
 - CNC Words: Two lists of 50 monosyllabic words at 60 dBA in the soundfield using a configuration of speech at 0° azimuth in quiet for the implanted ear (contralateral ear plugged)
 - AzBio Sentences in Noise at 60 dBA at +10 dB S0N0 presented in the soundfield for the everyday listening condition
 - Communication Documentation form
 - An anonymized .cdx file will be provided to the study sponsor
 - If the subject does **not** meet above criteria (≥ 30 CNC words) and AI has made modifications to the fitting and wants additional outcome measures, complete as requested.

- Complete patient reported COSI and SSQ-12
- Complete Clinician reported Materials/Tools questionnaire
- Complete clinician satisfaction questionnaire
- Complete subject Service Satisfaction Questionnaire
- Evaluate hearing options for contralateral ear
- CNC Words: Two lists of 50 monosyllabic words at 60 dBA in the soundfield using a configuration of speech at 0° azimuth in quiet for the implanted ear (contralateral ear plugged)
- AzBio Sentences in Noise at 60 dBA at +10 dB S0N0 presented in the soundfield for the everyday listening condition
- An anonymized .cdx file will be provided to the study sponsor.
- If CNC word score at 70 dB on speech audiometry remains less than 30% after completing the above steps, it is recommended the patient be seen in 1 month using standard clinical procedures using Custom Sound directed by CTM Cochlear staff.
- Traditional Model (Group B)
 - Programming and/or counselling as defined by Center
 - Communication documentation form
 - CNC Words: Two lists of 50 monosyllabic words at 60 dBA in the soundfield using a configuration of speech at 0° azimuth in quiet for the implanted ear
 - AzBio Sentences in Noise at 60 dBA at +10 S0N0 presented in the soundfield for the everyday listening condition with accessory is appropriate
 - Complete COSI, SSQ-12 and subject Service Satisfaction Questionnaire
 - An anonymized. cdx file will be provided to the study sponsor

6. Data Analysis

Statistical Analysis for this study is addressed in detail in the document entitled "Statistical Analysis Plan for the Evidence Based Delivery Model of Care for Newly Implanted Adult CI Recipients".

7. Summary of Data Collection Visits

Each subject will participate in 4-6 scheduled evaluation sessions. For Group A, subjects will be seen preoperatively, at switch-on and at 1, 3, 6 post activation. Visit windows are restricted for the switch on, 1, 3 and 6 month, and deviations from these intervals by more than the windows indicated in the table below.

Unscheduled visits should be documented on the form indicated above in section 5.3.1.4.

Table 1: Data Collection Visit Schedule Group A

Measure	Pre-Op	Switch - on	Video Conference (+/- 1 week)	1 mth (+/- 3 weeks)	3 mth (+/- 3 weeks)	6 mth (+/- 3 weeks)
Informed Consent	X					
Clinician Sat.						X
Hearing History	X					
Medical History	X					
Demographics	X					
Eligibility	X					
Device History	X					
Time measurement		X		X	X	X
Comm. Doc.			X	X	X	X

Form						
CNC Words	X				X	X
Az Bio +10	X					X
Usage Data				X	X	X
Service Satisfaction		X				X
SSQ	X					X
Rehab Screener				X		
COSI	X				X	X
Mat.-Tools Q.		X		X	X	X
AEs and DDs		X		X	X	X

For Group B, subjects will be seen preoperatively, at switch-on, 1-2 weeks, and at 1, 3, 6 post activation. Visit windows are restricted and deviations from these intervals by more than +/- 1 week for the video conference (Group A) and 1-2 week follow-up (Group B), and +/- 3 weeks for all other visits will be reported on in the clinical investigation report.

Unscheduled visits should be documented on the form indicated above.

Table 2: Data Collection Visit Schedule Group B

Measure	Pre-Op	Switch - on	1-2 weeks (+/- 1 week)	1 mth (+/- 3 weeks)	3 mth (+/- 3 weeks)	6 mth (+/- 3 weeks)
Informed Consent	X					
Clinician Sat.						X

Medical History	X					
Device History	X					
Hearing History	X					
Demographics	X					
Eligibility	X					
Time measurement		X	X	X	X	X
Comm. Doc. Form			X	X	X	X
Service Satisfaction		X				X
CNC Words	X				X	X
AzBio +10	X					X
Usage Data			X	X	X	X
SSQ	X					X
COSI	X				X	X
Mat.-Tools Q.		X		X	X	X
AEs and DDs		X	X	X	X	X

8. Reporting Process for Adverse Events and Device Deficiencies

